10.5 SAMPLE SIZE

The total number of subjects to be enrolled in the study is dependent upon the number of subjects who have completed the primary carfilzomib treatment protocols. It is anticipated that approximately 100 subjects will be enrolled in this study. Formal power calculation was not used to determine the sample size.

10.6 GUIDELINES FOR EARLY STUDY TERMINATION

Safety will be monitored throughout the trial. If any significant safety issues arise, the sponsor will be notified and if necessary, a decision to modify or terminate the study will be made.

11 REGULATORY OBLIGATIONS

11.1 INFORMED CONSENT

No Investigator may involve a human being as a subject in research unless the Investigator has obtained the legally effective informed consent of the subject or the subject's legally authorized representative. An Investigator shall seek such consent only under circumstances that provide the prospective subject or the subject's legally authorized representative sufficient opportunity to consider whether or not to participate, and that minimize the possibility of coercion or undue influence. The information that is given to the subject or the representative shall be in a language understandable to the subject or representative.

Onyx Therapeutics or its designated representative will provide the Investigator with a sample consent form. Local and/or institutional requirements may require disclosure of additional information in the informed consent. Any changes to the consent form must be submitted to the Onyx Therapeutics or its designated representative for approval, prior to submission to the IRB/IEC. The IRB/IEC will review the consent form for approval. A copy of the approved form must be submitted to the Onyx or its designated representative prior to initiation of the study.

Before implementing any study procedure, informed consent shall be documented by the use of a written consent form approved by the IRB/IEC and signed and dated by the subject or the subject's legally authorized representative at the time of consent. A copy of the signed

informed consent will be given to the subject or subject's legally authorized representative. The original signed consent must be maintained by the Investigator and available for inspection by Onyx Therapeutics, its designated representative, or regulatory authority at any time.

11.2 COMPLIANCE WITH LAWS AND REGULATIONS

The study will be conducted in accordance with US Food and Drug Administration (FDA) and International Conference on Harmonization (ICH) Guidelines for Good Clinical Practice (GCP), the Declaration of Helsinki, Health Canada, any applicable local health authority, and IRB or IEC requirements.

This study must have the approval of a properly constituted IRB or IEC. Before the investigational drug is shipped to the Investigator, the Investigator or designee will provide Onyx Therapeutics with a copy of the IRB/IEC approval letter stating that the study protocol and any subsequent amendments and informed consent form have been reviewed and approved.

The Investigator or designee will be responsible for obtaining annual IRB/IEC re-approval throughout the duration of the study. Copies of the Investigator's annual report to the IRB/IEC and copies of the IRB/IEC continuance of approval must be submitted to Onyx Therapeutics or designee.

The Investigator is also responsible for notifying their IRB/IEC of any significant AEs that are serious and/or unexpected.

Onyx Therapeutics will provide study sites with any Investigational New Drug (IND) safety reports generated, changes to the IB, and any safety updates. The Investigator is responsible for immediately notifying their IRB/IEC of any such updates.

Onyx Therapeutics will initiate in writing any substantive changes to this protocol as a protocol amendment. The amendment will be submitted to the IRB/IEC, together with a revised informed consent form, if applicable. Written documentation of IRB/IEC approval

must be received before the amendment is implemented. Upon completion of the trial, the Investigator must provide the IRB/IEC with a summary of the trial's outcome.

11.3 PRE-STUDY DOCUMENTATION REQUIREMENTS

Before the start of the study, the following documents must be on file with Onyx Therapeutics or its designated representative:

- An original US Form FDA 1572 or Canadian Qualified Investigator Undertaking Form (QIU) for the site, signed by the Principal Investigator
- Current Curriculum Vitae (CV) for the Principal Investigator and all Sub-Investigators
- Original financial disclosure forms for the Principal Investigator and all Sub-Investigators listed on the US Form FDA 1572 or Canadian QIU
- Current IRB/IEC membership list and/or Department of Health and Human Services number
- Copies of all appropriate laboratory certifications and laboratory normal ranges
- IRB/IEC approval of the protocol
 - The approval letter must identify the Onyx Therapeutics protocol number or title and date of protocol
- IRB/IEC-approved informed consent and approval letter
 - The approval letter must identify the Onyx Therapeutics protocol number or title of protocol and date of the informed consent
 - The informed consent must also be reviewed and approved by Onyx Therapeutics
- IRB/IEC approval of any advertising materials to be used for study recruitment, if applicable
 - Advertising materials must also be approved by Onyx Therapeutics
- Health Insurance Portability and Accountability Act (HIPAA) forms, if required
- Original signed Investigator agreement
- Original signed and dated protocol acceptance form

11.4 SUBJECT CONFIDENTIALITY

Subject medical information obtained as part of this study is confidential, and must not be disclosed to third parties, except as noted below. The subject may request in writing that medical information be given to his/her personal physician.

The Investigator/Institution will permit direct access to source data and documents by Onyx Therapeutics its designee, the FDA, Health Canada, and other applicable regulatory authorities. The access may consist of trial-related monitoring, audits, IRB/IEC reviews, and regulatory authority inspections, including FDA and Health Canada.

Release of research results should preserve the privacy of medical information and must be carried out in accordance with Department of Health and Human Services Standards for Privacy of Individually Identifiable Health Information, 45 Code of Federal Regulation (CFR) 164.508.

12 ADMINISTRATIVE AND LEGAL OBLIGATIONS

12.1 PROTOCOL AMENDMENTS AND STUDY TERMINATION

All protocol amendments will be implemented by Onyx Therapeutics and must receive IRB/IEC approval before implementation, except where necessary to eliminate an immediate hazard to subjects. The Investigator or designee must send a copy of the approval letter from the IRB, along with the revised informed consent form, to Onyx Therapeutics.

Both Onyx Therapeutics and the Investigator reserve the right to terminate the study according to the study contract. The Investigator or designee should notify the IRB/IEC in writing of the study's completion or early termination and send a copy of the notification to Onyx Therapeutics.

12.2 STUDY DOCUMENTATION AND ARCHIVES

12.2.1 *SOURCE DOCUMENTS*

Source records are original documents, data, and records (eg, medical records, raw data collection forms, pharmacy dispensing records, recorded data from automated instruments, laboratory data) that are relevant to the clinical trial. The Investigator will prepare and maintain adequate and accurate source documents. These documents are designed to record all observations and other pertinent data for each subject enrolled in this clinical trial. Source records must be adequate to reconstruct all data transcribed onto the CRFs.

12.2.2 CASE REPORT FORM COMPLETION

All required data must be recorded on the CRFs provided by Onyx Therapeutics or its designee. All CRFs must be completed by designated study personnel. The completed CRFs must be reviewed, signed, and dated by the Investigator or designee in a timely fashion.

12.2.3 ARCHIVAL OF RECORDS

According to 21 CFR 312.62(c), the Investigators shall retain records required to be maintained under this part for a period of 2 years following the date a marketing application is approved for the drug for the indication for which it is being investigated. If no application is to be filed or if the application is not approved for such indication, the Investigator shall retain these records until 2 years after the investigation is discontinued and the FDA, Health Canada, or applicable regulatory authorities are notified.

The Investigator must retain protocols, amendments, IRB/IEC approvals, copies of the Form FDA 1572 or Canadian QIU, signed and dated consent forms, medical records, CRFs, drug accountability records, all correspondence, and any other documents pertaining to the conduct of the study.

12.3 STUDY MONITORING AND DATA COLLECTION

Following prequalification and initiation of the study site, periodic monitoring visits will be made by Onyx Therapeutics, and/or its designated representative. The Investigator must provide sufficient space and allocate sufficient time for the monitor to inspect subject source records, CRFs, drug accountability records, and regulatory documents.

The purpose of trial monitoring is to verify the following:

- The rights and well-being of human subjects are protected.
- The reported data are accurate, complete, and verifiable from source documents.
- The conduct of the trial is in compliance with the currently approved protocol, amendment(s), ICH GCPs, FDA CFR, and any other applicable regulatory requirements.

The monitor shall submit a written report to Onyx Therapeutics after each trial site visit or trial-related communication. Reports shall include a summary of what the monitor reviewed

and significant findings, deviations and deficiencies, conclusions, actions taken or to be taken to ensure site compliance.

The Investigator must also permit trial-related audits, IRB/IEC review, and regulatory inspections providing direct access to data and source documents pertaining to this study if so requested.

The following steps will be taken to ensure the accuracy, consistency, completeness, and reliability of the data:

- Routine study site monitoring
- CRF review against source documents
- Data management quality control checks
- Sponsor medical review

A contract research organization (CRO) will be responsible for the data management of this clinical trial. Onyx Therapeutics or its designee will be responsible for the design and distribution of the CRFs. Onyx Therapeutics or its designee will be responsible for the monitoring of the CRFs. CRFs will be returned to the CRO. The CRO, and/or Onyx Therapeutics, and/or its designee will generate queries in the event of incomplete or inconsistent data to be reconciled by the study site.

APPENDIX A: SCHEDULE OF EVENTS

Visit	Screening (Day -30 to -1)	Cycle 1	Every Cycle	Cycle 3 and Every 3 Cycles	End of Study (Within 30 days of last dose of study drug)
Written Informed Consent	X				
Inclusion/Exclusion Criteria	X				
Obtain Previous PX-171 Protocol Unique Identifier	X				
Pregnancy Test ¹	X				
Routine Physical Examination	X				X
Height, Weight, and BSA ²	X		Day 1		
ECOG Performance and Neuropathy Grade	X				
Bone Marrow Sample for Cytogenetics and FISH ³	X				X
CBC + Platelet Count and Serum Chemistry ⁶		Day 1	Day 1	Day 1	
Carfilzomib Dosing (the same dose level and frequency as administered at the last visit of the prior Onyx study)		Days 1, 2, 8, 9, 15, 16, or same dose level and frequency as prior study	Days, 1, 2, 8, 9, 15, 16, or same dose level and frequency as prior study	Days, 1, 2, 8, 9, 15, 16, or same dose level and frequency as prior study	
Disease Assessments (Extent of disease measurements and response), per method employed in previous protocol ⁴	X			Day 1	X
Peripheral Neuropathy AEs (all Grades)	X	X	X	X	X
Grade 3 and 4 AEs, SAEs or AEs Resulting in Missed Dose or Dose Reduction (all Grades) ⁵	X	X	X	X	X
Record any concomitant chemotherapy reagent	X	X	X	X	X

1 Females of childbearing potential must have a negative serum or urine pregnancy test, with a sensitivity of at least 50 mIU/mL, within 3 days prior to dosing.

2 Height done at screening visit only; BSA calculated Day 1 of every cycle. However, dose adjustments not needed for weight gains/losses of $\leq 20\%$.

3 Screening bone marrow aspirate or biopsy for cytogenetics and FISH is optional and is for MM subjects whose disease status at study entry is PR or less. A Bone marrow sample is also optional for all MM subjects at the end of study if there is evidence of disease progression.

4 If disease assessments are done previously within 30 days of first dose of extended study drug, they will not be required again at screening. If disease assessments per standard institutional practices occur more frequently than every 3 months (eg, every month or every 2 months), the most recent assessment may be reported.

5 Record all AEs leading to missed dose, dose reduction or discontinuation. Record all Grade 3 and 4 AEs from time of consent through 30 days post last administered dose of study drug or initiation of a new anti-cancer therapy.

6 CBC + Platelet Count and Serum Chemistry data will not be routinely recorded on CRFs.

**Appendix B: ECOG Performance Scale
(Eastern Cooperative Oncology Group)**

Grade	Description
0	Normal activity, fully active, able to carry on all pre-disease performance without restriction.
1	Symptoms, but fully ambulatory, restricted in physically strenuous but ambulatory and able to carry out work of a light or sedentary nature (eg, light housework, office work).
2	Ambulatory and capable of all self-care but unable to carry out any work activities. Up and about more than 50% of waking hours.
3	Capable of only limited self-care, confined to bed or chair more than 50% of waking hours.
4	Completely disabled. Cannot carry on any self-care. Totally confined to bed or chair.
5	Death

APPENDIX C: NCI CTCAE VERSION 3.0

Common Terminology Criteria for Adverse Events (CTCAE) of the National Cancer Institute (NCI) Version 3.0

Publish Date: December 12, 2003

<http://ctep.cancer.gov/forms/CTCAEv3.pdf>

APPENDIX D: INTERNATIONAL UNIFORM RESPONSE CRITERIA FOR MULTIPLE MYELOMA

Summary Table	
Response Subcategory	Response Criteria
sCR	CR as defined below plus normal FLC ratio and absence of clonal cells in bone marrow by immunohistochemistry or immunofluorescence. ¹
CR	Negative immunofixation on the serum and urine, disappearance of any soft tissue plasmacytomas, and < 5% plasma cells in bone marrow
VGPR	Serum and urine M-protein detectable by immunofixation but not on electrophoresis or 90% or greater reduction in serum M-protein with urine M-protein level < 100 mg per 24 hours
PR	
≥ 50% reduction of serum M-protein and reduction in 24 hour urinary M-protein by ≥ 90% or to < 200 mg per 24 hours
 
If the serum and urine M-protein are unmeasurable, a ≥ 50% decrease in the difference between involved and uninvolved FLC levels is required in place of the M-protein criteria.
 
If serum and urine M-protein and serum FLC are unmeasurable,² then ≥ 50% reduction in plasma cells is required in place of M-protein, provided baseline bone marrow plasma cell percentage was ≥ 30%
 
In addition to the above listed criteria, if present at baseline, a ≥ 50% reduction in the size of soft tissue plasmacytomas is also required

SD	Not meeting criteria for CR, VGPR, PR, MR or PD
PD	
Progressive Disease requires any one or more of the following:
 
Increase of ≥ 25% from baseline in:
 
 --- serum M-component and /or (the absolute increase must be ≥ 0.5 g/dL) --- urine M-component and/or (the absolute increase must be ≥ 200 mg/24 h) 
Only in subjects without measurable serum and urine M-protein levels: the difference between involved and uninvolved FLC levels. The absolute increase must be > 10 mg/dL.
 
Bone marrow plasma cell percentage: the absolute % must be ≥ 10%
 
Definite development of new bone lesions or soft tissue plasmacytomas or definite increase in the size of existing bone lesions or soft tissue plasmacytomas
 
Development of hypercalcaemia (corrected serum calcium > 11.5 mg/dL or 2.65 mmol/L) that can be attributed solely to the plasma cell proliferative disorder

Source: Durie BG, Harousseau JL, Miguel JS, Bladé J, Barlogie B, Anderson K, et al. International uniform response criteria for multiple myeloma. Leukemia 2006 Sep;20(9): 1467–73. Errata in: Leukemia 2006 Dec;20(12):2220. Leukemia 2007 May;21(5):1134.

¹ Presence/absence of clonal cells is based upon the κ/λ ratio. An abnormal κ/λ ratio by immunohistochemistry and/or immunofluorescence requires a minimum of 100 plasma cells for analysis. An abnormal ratio reflecting presence of an abnormal clone is κ/λ of > 4:1 or < 1:2.

² Measurable disease: serum M protein ≥ 1 g/dL, urine M-protein > 200 mg/24 h, or serum involved FLC levels > 10 mg/dL with a normal κ/λ ratio.

All response categories require 2 consecutive assessments made at any time before the institution of any new therapy; all categories also require no known evidence of progressive or new bone lesions if radiographic studies were performed. Radiographic studies are not required to satisfy these response requirements.

Minimal Response	
Response Subcategory	Response Criteria
MR	
25%–49% reduction in the level of serum M-protein or a 50%–89% reduction in 24 hours urinary M-protein, which still exceeds 200 mg/24 h, maintained for a minimum of 6 weeks.
 
For subjects with non-secretory myeloma only, 25%–49% reduction in plasma cells in a bone marrow aspirate and on trephine biopsy, if biopsy is performed, maintained for a minimum of 6 weeks.
 
25%–49% reduction in the size of soft tissue plasmacytomas (by radiography or clinical examination)

Source: Bladé J, Samson D, Reece D, Apperley J, Björkstrand B, Gahrton G, et al. Criteria for evaluating disease response and progression in subjects with multiple myeloma treated by high-dose therapy and haemopoietic stem cell transplantation. Myeloma Subcommittee of the EBMT. European Group for Blood and Marrow Transplant. Br J Haematol 1998 Sep; 102(5):1115–23.

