10.4.2 DISEASE RESPONSE ANALYSIS

The analysis of disease response will be based on the FAS populations defined in [Section 10.3.2](#). The assessment of disease response will be based on duration of OS, PFS, and TTP. For patients previously enrolled in PX-171-008, response may be first noted in PX-171-010. Durations will be calculated from the date of disease response documented in the subjects' prior carfilzomib protocol, or in PX-171-010 for subjects previously enrolled in PX-171-008, to the first documentation of the endpoint's occurrence in the extended trial.

Depending on the completeness of the available follow-up data, analysis of each endpoint will be performed based on the Kaplan-Meier method. The date of progression will be determined using the progression criteria described in [Appendix D–E](#). The date of censoring for subjects who end the study without documented progression will correspond to the date the last disease assessment was performed. Analysis will be performed separately by disease cohort (MM or solid tumor).

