5.5 Baseline

If subjects had not received other anti-cancer therapies and not reached progressive disease when they enrolled in study 010, baseline disease assessments from the initial study will be used for baseline values for determining response and progression unless no prior assessments were collected (eg, PX-171-008). For those subjects who didn't have baseline collected in prior study, tumor assessments will be conducted at the time of screening for the current study using the appropriate method. And for those who received other anti-cancer therapies and/or progressive disease when they enrolled in study 010, baseline values from current study will be used.

During the study, the addition of certain approved agents with known antitumor activity or increase of carfilzomib dose and/or frequency is permitted if there is concern for disease progression and per Investigator discretion in consultation with the Onyx Medical Monitor. If it happens, measurements at the time of addition of new agents will be used as new baseline.

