7.3 Demographic and Baseline Characteristics

The following demographic and baseline characteristics will be summarized by both disease cohorts and overall unless otherwise indicated. Summary statistics will be tabulated based on the Safety population.

- Both Disease Cohorts
 - Age at the entry of PX-171-010: <65, \geq 65
 - Sex: female, male
 - Race: Caucasian, African American, Hispanic, Asian/pacific islander
 - Time since diagnosis (years) in PX-171-010
 - Clinical response assessment at entry of PX-171-010
- MM Cohort
 - Height (cm), weight (kg), body surface area (BSA), ECOG performance status, Neuropathy Grade (All data from time of entry in PX-171-010 except ECOG which is from the time of entry in initial study and entry in PX-171-010.)
 - Number of prior regimens (initial study)
 - Prior Bortezomib (initial study)
 - M-protein light chain isotype and heavy chain isotype (initial study and PX-171-010)
 - Measurable disease category (initial study)
 - Refractory status (initial study)

- Plasma cell involvement (<50%, >=50%) (initial study)
- Cytogenetics (initial study): normal/favorable, poor prognosis, unknown or not done
- FISH (initial study): normal/favorable, poor prognosis, unknown or not done
- Cytogenetics or FISH (initial study): normal/favorable, poor prognosis, unknown or not done
- Serum Beta-2 Microglobulin (mg/L) (initial study)
- Durie-Salmon Staging and Subclassification (initial study)
- Did the subject maintain the parent study's response until PX-171-010 enrollment?
- Did the subject meet IMWG criteria for disease progression until PX-171-010 enrollment?
- Solid Tumor Cohort
 - Tumor type (initial study)

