7.7.2 Progression Free Survival (PFS)

PFS is defined as number of days between start of treatment and first evidence of documented disease progression or death (due to any cause), whichever occurs first. Disease progression will be determined by the local investigator for regimens with the same baseline using the International Uniform Response Criteria ([Durie et al. 2006, with corrections](#)) (IMWG-URC) for multiple myeloma subjects and RECIST criteria ([Therasse et al. 2000](#)) for solid tumor subjects. PFS will be re-calculated whenever the baseline is reset due to addition of new anti-cancer therapy or increase of carfilzomib dose/frequency:

- 1) For regimens that continue from initial study without baseline being reset, if subjects didn't progress before PX-171-010, then PFS for the period from initial study to PX-171-010 study will be calculated as Disease Progression /Death Date – Date of first dose in initial study + 1 day, and PFS for the period of PX-171-010 study only will be calculated as Disease Progression /Death Date – Date of first dose in PX-171-010 + 1 day.
- 2) For regimens that start in PX-171-010 study with baseline being reset from initial study or previous regimens, PFS will be calculated as Disease Progression /Death Date –

Date of first dose in the first regimen among the regimens with common baseline + 1 day.

PFS will be right-censored for subjects who met one of the following conditions: 1) no baseline disease assessments or any post-baseline assessments, 2) alive and does not have documentation of disease progression before a data analysis cutoff date. The PFS censoring rules are described in Table 1.

Table 1. Censoring Rules for PFS Analysis

Situation	Date of Progression or Censoring	Outcome
No baseline disease assessments or any post-baseline assessments	Date of first dose	Censored
Alive and without documentation of disease progression	Date of last disease assessment	Censored
Death or disease progression between planned disease assessments	Date of death or first disease assessment showing disease progression, whichever occurs first	Progressed
Death or PD immediately after more than 1 consecutively missed disease assessment visit*	Date of last disease assessment before the first missed visit	Censored
Death before first disease assessment	Date of death	Progressed

* If death or PD is more than 168 days after previous disease assessment, or the first dosing date if there is no previous disease assessment.

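### Myeloma M-protein progression is referenced to the initial-study baseline for subjects who enter progression-free; followed literally, responders' PFS and TTP events can come late, and the documents do not settle which reference is used

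*Protocol*

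**What the plan says.** - **Progression criteria.** Protocol 10.4.2: "The date of progression will be determined using the progression criteria described in" Appendices D and E. In Appendix D the myeloma PD row opens with "Increase of ≥ 25% from baseline in", followed by the serum component (absolute rise at least 0.5 g/dL) and the urine component (at least 200 mg/24 h). No lowest value is mentioned.
- **Which baseline.** SAP 5.5 applies its default to this group: "If subjects had not received other anti-cancer therapies and not reached progressive disease when they enrolled in study 010". For them, provided prior assessments exist, "baseline disease assessments from the initial study will be used for baseline values for determining response and progression". Subjects with PD or other therapy at entry use the PX-171-010 baseline.
- **Status at entry.** SAP 7.3 tabulates "Did the subject meet IMWG criteria for disease progression until PX-171-010 enrollment".
- **Reset during the study.** Under SAP 5.5, adding agents or increasing carfilzomib dose or frequency is "permitted if there is concern for disease progression", and then "measurements at the time of addition of new agents will be used as new baseline". SAP 7.7.2 adds: "PFS will be re-calculated whenever the baseline is reset due to addition of new anti-cancer therapy or increase of carfilzomib dose/frequency". SAP 7.7.3 does the same for TTP.
- **Who decides.** Protocol 7.8 tells investigators to use the parameters of the subject's previous study. SAP 7.7.2 names the published myeloma criteria with their corrections. SAP 7.7 takes the investigator's assessment from the CRF.
- **Solid tumors.** Appendix E measures partial response from the baseline lesion sum, but progression from the smallest sum seen on treatment.

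**The concern.** For solid tumors the protocol keeps two references apart: baseline for response, lowest value for progression. For myeloma, the Appendix D wording and SAP 5.5 together use one reference for both, and it is the level before any carfilzomib was given. A subject who responded well in the parent study could relapse back to that level and still not meet the M-protein criterion.

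Such subjects are expected: the synopsis provides for myeloma subjects entering in sCR, CR, VGPR, PR or MR. PFS and TTP are two of the three secondary endpoints and the only ones given Kaplan-Meier estimates, since SAP 7.7.1 limits OS to a listing. Protocol section 8 dates PD, for subjects withdrawn for it, by the laboratory test or procedure that shows it, so the reference value bears directly on the event date. If a subject leaves before the higher threshold is reached, Table 1 turns what could have been an event into a censored time. The PX-171-010-only versions of PFS and TTP start at the first dose in this study but, for these subjects, still judge progression against the older baseline.

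**Working it through.** The documents give no median PFS or TTP, event count or power figure to reproduce. The check compares thresholds.

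**Inputs from the documents:** 25% rise; minimum rise 0.5 g/dL (serum) or 200 mg/24 h (urine); PR is a serum fall of at least 50%, and one route to VGPR is a fall of at least 90%; serum disease is measurable from 1 g/dL; assessments every 3 cycles of 28 days, or 84 days.
**Assumed:** baselines of 1 to 5 g/dL; for timing only, exponential regrowth, a doubling time, and M-protein as the first route to PD.

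**Serum threshold:** t(r) = max(1.25r, r + 0.5), with r either the initial-study baseline or the lowest value on treatment.

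| Baseline (g/dL) | t(baseline) | 50% fall: lowest, t, ratio | 90% fall: lowest, t, ratio |
|---|---|---|---|
| 1.0 | 1.50 | 0.5, 1.00, 1.50 | 0.1, 0.60, 2.50 |
| 2.0 | 2.50 | 1.0, 1.50, 1.67 | 0.2, 0.70, 3.57 |
| 3.0 | 3.75 | 1.5, 2.00, 1.88 | 0.3, 0.80, 4.69 |
| 5.0 | 6.25 | 2.5, 3.13, 2.00 | 0.5, 1.00, 6.25 |

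Urine, with max(1.25r, r + 200), after a 90% fall from 500, 1000 or 2000 mg/24 h: 700 against 250, 1250 against 300, 2500 against 400.

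**Direction.** t(r) rises with r, and the lowest value (baseline included) cannot exceed the baseline. So t(lowest) ≤ t(baseline), with equality only when there is no fall. The literal M-protein date is the same or later, never earlier.

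**Timing, as illustration only.** Delay = doubling time × log2(ratio). At baseline 3.0 this is log2(1.88) = 0.91 doubling times after a 50% fall and log2(4.69) = 2.23 after a 90% fall. With a 90-day doubling time that is about 82 and 201 days. The visit grid can absorb it: with a 2-month doubling time and a 50% fall the delay is 0.907 × 60.9 = 55 days, and both rules land on the same visit in about 1 − 55.2/84 = 34% of cases.

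**Reset.** Baseline 3.0, lowest 0.3, agent added at 2.0 on suspicion of progression. The value is past 0.80 but short of 3.75, so on the literal reading the first regimen has no M-protein event. The new baseline is 2.0 and the next threshold 2.50. Table 1 has no row for a reset; only its general row, for subjects alive with no documented progression, fits the earlier period, and that row censors.

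**Entry, if the same wording is applied there.** Baseline 3.0, lowest 0.3, value at entry 1.5. From baseline: not PD, initial baseline kept, threshold 3.75. From the lowest value: already PD (0.80 passed), baseline becomes 1.5, threshold 2.00. The choice also decides which SAP 7.7.2 formula applies.

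**The case against.** The strongest reply is that no programmed derivation from M-protein is planned. The analysis uses what the investigator recorded, and investigators are pointed to parent-study parameters and to the published criteria with corrections. If those use another reference, the delay may never occur. This stands: the documents do not show that the estimates will be biased. It does not remove the defect, because SAP 5.5 would then conflict with the criteria actually applied, and PD dating could be inconsistent across subjects.

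A second reply is that the lowest-value reference appears only in the solid-tumor criteria, which come from a different publication, and that two sets of criteria may differ. That is fair. Late here means relative to a lowest-value reference; what the myeloma publication says is not in the documents and is not relied on.

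Third, the reset is partly handled, since PFS and TTP are recalculated by regimen, and the gap exists under any PD reference. Agreed. Escalations that follow documented progression, which Protocol 1.5 describes, are unaffected. What remains is censoring triggered by suspected progression, with no count and no sensitivity analysis.

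A reader might also infer that most continuing subjects are affected. The documents do not support this: PD at entry is not an exclusion, those subjects move to the current-study baseline, and no split is given.

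**Conclusion.** The point holds as a conditional one. Followed literally, Appendix D with SAP 5.5 requires a myeloma responder who keeps the initial-study baseline to exceed the pre-treatment M-protein by 25% and by 0.5 g/dL. Over assumed baselines of 1 to 5 g/dL, that threshold is 1.5 to 2.0 times the lowest-value threshold after a 50% fall and 2.5 to 6.3 times after a 90% fall. M-protein events for PFS and TTP are then the same or later, unless lesion, plasmacytoma or calcium criteria, or death for PFS, come first. Without a fall there is no difference.

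Two stronger readings go too far. One is that reported PFS and TTP will be too long: that depends on which reference investigators used, which the documents leave open. The other is that the delays in days are expected effects: they rest on assumed baselines and regrowth rates.

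The study tests no hypothesis and its primary endpoint is safety, so the consequence is confined to descriptive efficacy estimates in the myeloma cohort. It is still worth correcting, because a stated rule, and not merely a missing detail, can produce late or missing events.

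**What to change.** For the analysis only:

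1. In SAP 5.5, 7.7.2 and 7.7.3, state one myeloma progression reference and reconcile it with Protocol 7.8 and 10.4.2 and with the criteria cited in SAP 7.7.2. Keep the investigator's CRF assessment as planned. Add supplementary PFS and TTP derived from recorded values, with the reference being the lowest value since and including the applicable baseline (initial-study, or the new one after a reset), and keep the stated absolute minimum rises. Including the baseline protects non-responders: with baseline 2.0 and lowest later value 2.4, the threshold stays at 2.50 and does not become 3.00.
2. State how the earlier regimen is handled when baseline is reset without documented PD: censor at the last assessment before the reset. Report the number of such subjects and add a sensitivity analysis that counts the reset as an event.
3. Apply the same stated reference to PD status at entry, where it selects the baseline and the PFS and TTP formula.

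The cost is SAP wording, one row in Table 1 and a second derivation. The derivation needs visit-level data from the parent studies, where many of the lowest values may lie. Estimates may be shorter, and some lowest values may be missing because Protocol 7.6 lets sites report only the most recent assessment. Appendix D also bears on stopping treatment (Protocol 3.4 and section 8); the sponsor must reconcile those passages, and no clinical rule is proposed here.
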